| Treatment consent | | X | | | | |
| Review of medical record | X | | | | | |
| Confirmation of resection | X | | | | | |
| H&P, PS, wt | | X | X | | X | |
| CBC | | X | X | | | |
| CMP, LDH, amylase, lipase | | X | X | | | |
| TSH, free T3 or total T3, free T4 | | X | X | | | |
| INR, aPTT ⁹ | | X | | | | |
| EBV serology | X ¹¹ | | | | | |
| HIV serology | X ¹¹ | | | | | |
| HBV serology | X ¹¹ | | | | | |
| HCV serology | X ¹¹ | | | | | |
| Pregnancy test ³ | | X | X | | | |
| Urinalysis reflex to micro and/or culture ⁹ | | X | | | | |
| ECG | | X | X ¹² | | | |
| Randomization ⁶ | | X | | | | |
| Blood for ctDNA (Signatera testing) | | X ⁵ | X ⁸ | | X ¹⁰ | |
| Whole blood and tissue for whole exome sequencing (for design of Signatera assay) | X ¹³ | | | | | |
| Atezolizumab | | | X ⁴ | | | |
| Tiragolumab ⁷ | | | X ⁴ | | | |
| CT scan | | X | | X ² | | X |
| AE assessment | | | Baseline through 90 days after last day of treatment | | | |

1. corresponds with the end of every 3rd cycle; if there are treatment delays, imaging should continue to be done every 12 weeks rather than waiting for the end of every 3rd cycle

2. Q12W during Years 1 and 2 after surgery, Q24W during Year 3 after surgery; depending on when a patient discontinues treatment, follow-up may be Q12W or Q24W; follow-up will discontinue after 3 years have elapsed from date of surgery

3. women of childbearing potential only

4. treatment can continue for up to 13 cycles; refer to Section 5.2 for instructions regarding monitoring of vital signs and post-infusion observation

5. must take place 4-12 weeks after surgery; if ctDNA positive, patients will be randomized to receive either atezolizumab and tiragolumab or atezolizumab monotherapy, and if ctDNA negative, patient will not continue in this study

6. stage 1 only; randomization must occur no more than 16 weeks after date of surgery

7. if randomized to receive tiragolumab during stage 1; all patients during stage 2.

8. prior to dosing on C3D1, C6D1, C9D1, C12D1 – the collection of blood for ctDNA should be discontinued after 2 consecutive negative tests

9. required at Step 2 screening and thereafter only as clinically indicated

10. optional

11. may take place up to 42 days prior to C1D1
12. ECG should be performed at Step 2 screening, C3D1, C6D1, C9D1, and C12D1

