1.2 Circulating Tumor DNA and Risk of Relapse

In the evolving paradigm of effective adjuvant therapy in melanoma, it is essential to develop biomarkers identifying patients at high risk of relapse. Currently, features of the primary tumor such as ulceration, Breslow and number of mitoses in addition to nodal classification and disease stage are with a poor outcome in stages I–III melanoma; however, patient numbers in these studies were small and have yet to be confirmed in larger cohorts^{6,7}.

Lee et al. showed that detecting circulating tumor DNA (ctDNA) in plasma taken within 12 weeks of curative intent surgery is highly predictive of relapse in patients with stage II/III melanoma. The majority of patients with detectable ctDNA relapsed within 1 year of surgery, suggesting that ctDNA in the plasma can reveal occult metastatic disease that is not evident on radiological imaging. Notably, they were able to identify melanoma patients at high risk of both distant metastatic relapse and local recurrence, which is consistent with studies showing that ctDNA can signal micrometastatic disease after neoadjuvant chemotherapy postsurgical resection in breast cancer and following surgery for stage II colorectal cancer⁸

In the same study, ctDNA was independent of standard staging indices in predicting disease recurrence, demonstrating the value of this approach in melanoma.

The ability to predict progression to stage IV disease is extremely important in light of recent findings that immune checkpoint inhibition improves RFS in stage III melanoma. Detection of ctDNA allows identification of a subgroup of patients at high risk of early relapse and inferior survival, allowing stratification of patients to adjuvant regimens associated with higher toxicity but greater potential for efficacy. Taken at a single time-point following surgery, it can add to AJCC staging in informing individual prognosis and therefore discussion regarding risks and benefits of adjuvant therapy, while longitudinal sampling will likely improve the ability to detect disease progression before radiological imaging.

We advocate that the findings from Lee et al. be confirmed in clinical trials investigating treatment responses in this population in order to evaluate whether it is also a predictive biomarker for response to immune or targeted therapy.

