| To determine the relapse-free survival in patients with stage II melanoma who test positive for circulating tumor DNA and are treated with atezolizumab and tiragolumab, and those who are treated with atezolizumab alone | Relapse-free survival (RFS), defined as the duration of time from the date of randomization to the date of earliest disease relapse or death, whichever occurs first. | RFS is an acceptable measure of clinical benefit for a late stage study that demonstrates superiority of a new antineoplastic therapy, especially if the magnitude of the effect is large and the therapy has an acceptable risk/benefit profile. |
| To determine the distant metastasis-free survival in patients with stage II melanoma who test positive for circulating tumor DNA and are treated with atezolizumab and tiragolumab, and those who are treated with atezolizumab alone (both circulating tumor DNA positive and negative). | Distant-metastasis free survival (DMFS), defined as the duration of time from the date of positive ctDNA being confirmed to the date of appearance of a distant metastasis or death, whichever occurs first. | The secondary efficacy objective of this study is to compare DMFS between the two treatment arms |
| To determine the overall survival of patients with stage II melanoma. | Overall survival (OS), defined as the duration of time from the date of positive ctDNA being confirmed to death from any cause. | The secondary efficacy objective of this study is to compare OS between the two treatment arms |
| To evaluate the safety and tolerability of atezolizumab | Defined as the number of treatment-related grade 3 or | Safety parameters commonly used for |

| | | |
|--|--|--|
| and tiragolumab in patients with stage II melanoma. | greater AEs and discontinuations due to treatment-related AEs. | evaluating investigational systemic anticancer treatments are included as safety endpoints including, but not limited to, the incidence of, causality, and outcome of AEs/serious adverse events (SAEs); and changes in vital signs and laboratory values. Adverse events will be assessed as defined by CTCAE, Version 5.0. |
| To assess the impact of ctDNA kinetics on outcomes (relapse-free survival, distant metastasis-free survival, and overall survival) in patients with surgically resected stage II melanoma. | | |

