3.2 Step Two (Randomization and Treatment) Eligibility

3.2.1 Inclusion Criteria

1. Positive ctDNA test.
2. Normal bone marrow and organ function as defined below:
 - a. Absolute neutrophil count $\geq 1,500/\text{mcL}$
 - b. Lymphocyte count $\geq 500/\text{mcL}$
 - c. Platelets $\geq 100,000/\text{mcL}$
 - d. Hemoglobin ≥ 9.0 g/dL (patients may be transfused to meet this criterion)
 - e. Total bilirubin ≤ 1.5 x IULN or direct bilirubin \leq IULN for participants with total bilirubin levels > 1.5 x IULN; patients with known Gilbert disease must have total bilirubin ≤ 3 x IULN
 - f. AST(SGOT)/ALT(SGPT) ≤ 2.5 x IULN
 - g. Alkaline phosphatase ≤ 2.5 x IULN
 - h. Creatinine clearance ≥ 45 mL/min by Cockcroft-Gault
 - i. Serum albumin ≥ 2.5 g/dL
 - j. INR or PT ≤ 1.5 x IULN unless participant is receiving anticoagulant therapy as long as PT or aPTT is within therapeutic range of intended use of anticoagulants
 - k. aPTT ≤ 1.5 x IULN unless participant is receiving anticoagulant therapy as long as PT or aPTT is within therapeutic range of intended use of anticoagulants
3. ECOG performance status ≤ 1 (see Appendix A)

4. The effects of atezolizumab and tiragolumab on the developing human fetus are unknown. For this reason, women of childbearing potential and men must agree to use adequate contraception (hormonal or barrier method of birth control, abstinence) prior to study entry and for the duration of study participation, for 90 days after the final dose of tiragolumab, and for 5 months after the final dose of atezolizumab. Should a woman become pregnant or suspect she is pregnant while participating in this study, she must inform her treating physician immediately. Men treated or enrolled on this protocol must also agree to use adequate contraception prior to the study, for the duration of the study, and 90 days after completion of the study

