11.0 MEASUREMENT OF EFFECT

Tumor imaging is strongly preferred to be acquired by CT. For the abdomen and pelvis, contrast-enhanced MRI may be used when CT with iodinated contrast is contraindicated, or when mandated by local practice. The same imaging technique regarding modality, ideally the same scanner, and the use of contrast should be used in a participant throughout the study to optimize the reproducibility of the assessment of existing and new tumor burden and improve the accuracy of the assessment of response or progression based on imaging.

For the purposes of this study, patients should be re-evaluated every 12 weeks (+/- 2 weeks) for the first two years then every 24 weeks (+/- 2weeks) x2 for the third year, in addition to a baseline scan.

Relapse-free survival is defined as the time from randomization to any of the following events:

recurrence of melanoma at any site (local, in-transit or regional lymph nodes or distant recurrence) or death due to any cause. New incident cases of melanoma and second cancer diagnoses are not counted as events for recurrence-free survival.

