14.3 Secondary Endpoints

- Confirmed ctDNA negative rate, defined as the proportion of ctDNA-positive patients having two consecutive negative ctDNA tests.
- Relapse free survival (RFS), defined as the duration of time from the date of positive ctDNA being confirmed to the date of earliest disease relapse or death, whichever occurs first. Patients who neither relapse nor die by the data cutoff date will be censored at the last follow up date.
- Distant metastasis free survival (DMFS), defined as the duration of time from the date of positive ctDNA being confirmed to the date of appearance of a distant metastasis or death, whichever occurs first. Patients who neither develop distant metastasis nor die by the data cutoff date will be censored at the last follow up date.
- Overall survival (OS), defined as the duration of time from the date of positive ctDNA being confirmed to death from any cause. Patients who are alive by the data cutoff date will be censored at the last follow up date.

- Safety and tolerability will be defined as the number of treatment (i.e., atezolizumab and tiragolumab) related grade 3 or greater adverse events (AEs). Adverse events will be assessed using CTCAE v5.0 criteria. Safety will be monitored from the time of initiation of study treatment to 30 days after discontinuation of therapy.

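### RFS, DMFS and OS in section 14.3 start at ctDNA confirmation, before Step Two entry, so the level of the curves is biased upward; RFS also has two conflicting start dates

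*Combined protocol and SAP*

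**What the plan says.** Section 14.3 gives the three time-to-event endpoints the same origin: "Relapse free survival (RFS), defined as the duration of time from the date of positive ctDNA being confirmed", "Distant metastasis free survival (DMFS), defined as the duration of time from the date of positive ctDNA being confirmed" and "Overall survival (OS), defined as the duration of time from the date of positive ctDNA being confirmed to death from any cause". Section 2.0 agrees for DMFS and OS but not for RFS: "Relapse-free survival (RFS), defined as the duration of time from the date of randomization". Section 11.0 also starts RFS at randomization: "Relapse-free survival is defined as the time from randomization to any of the following events".

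The first Step Two inclusion criterion in section 3.2.1 is "Positive ctDNA test". Section 4.0 sets the blood draw at 4 to 12 weeks after resection, and footnote 6 of the Schedule of Activities adds that "randomization must occur no more than 16 weeks after date of surgery". Section 14.6 describes the analysed groups as treated patients, 43 on the combination and 18 on monotherapy if the trial continues to stage 2. Section 14.7 specifies Kaplan-Meier curves and a log-rank test between the groups. It mentions no delayed entry or landmark. Section 14.5 states that stage 2 is not randomized.

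**The concern.** Between a positive result and Step Two entry a patient must stay alive, pass the laboratory, performance status, infection and surgery criteria, and have a CT. Someone who dies in that interval cannot be among the treated patients. Someone whose CT shows overt disease is unlikely to be. Yet section 14.3 counts the interval as follow-up for those who do enter. This is left truncation (immortal time) that a plain Kaplan-Meier estimate does not correct.

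Section 14.1 says that the combination arm is to be read as a one-armed study, so the level of its curves is what readers will take away. The protocol's rationale is early relapse: "The majority of patients with detectable ctDNA relapsed within 1 year of surgery" (section 1.2). A guaranteed event-free start distorts the early part of the curve most.

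The RFS conflict adds to this. Under section 2.0, a stage 1 patient whose first relapse is distant would have two different times, RFS and DMFS, for the same event. A stage 2 patient would have no RFS start date at all.

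**Working it through.** **The plan's own figure.** The only sized quantity is the Simon design for ctDNA clearance (10% against 25%). An exact search returns the stated design: stop at 2 or fewer of 18, promising at 8 or more of 43. Attained one-sided alpha is 0.0480, power 0.8003, and expected sample size under the null 24.7. It does not depend on the survival clocks, and no DMFS or OS event count or power is stated.

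**Length of the gap.**
- Draw at week 4, randomization at week 16: 16 − 4 = 12 weeks from the draw. Counted from the result, it is shorter by the laboratory turnaround, which is not stated, so it is just under 12 weeks.
- Draw at week 12: 16 − 12 = 4 weeks at most, less turnaround.
- The Schedule of Activities allows Step 2 screening up to 28 days before C1D1 except where noted, and the ctDNA draw stands in that column. If the limit applies to the draw, the gap is never more than 4 weeks. Footnote 5 gives the draw its own window and may be such an exception; the text does not settle this.

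**Size of the shift.** Assume a constant hazard λ, with λ = −ln S(T)/T, and a gap of g years (weeks divided by 52.18).
- True curve: S(t) = exp(−λt).
- Curve under the plan, for t > g: exp(−λ(t − g)) = S(t) × exp(λg).

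Example: true 12-month DMFS of 50% gives λ = 0.693 per year. With g = 4/52.18 = 0.0767, the curve shows 0.50 × exp(0.0531) = 0.527, a shift of 2.7 points.

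Shift at 12 months, in percentage points:

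| Assumed truth | 4-week gap | 8-week gap | 12-week gap |
|---|---|---|---|
| DMFS 50% at 12 months | 2.7 | 5.6 | 8.6 |
| DMFS 80% at 12 months | 1.4 | 2.8 | 4.2 |
| OS 82% at 5 years (stage IIC, section 1.1) | 0.3 | 0.6 | 0.9 |
| OS 94% at 5 years (stage IIA, section 1.1) | 0.1 | 0.2 | 0.3 |
| OS 90% at 12 months | 0.7 | 1.5 | 2.2 |

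The documents give no DMFS hazard and no gap distribution, so the DMFS rows and the last OS row are assumptions. The section 1.1 OS rates are for stage II overall, not for ctDNA-positive patients. The formula applies equally to RFS as defined in section 14.3.

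**Comparison between arms.** Log-rank tests were simulated under no treatment effect: 10,000 runs per setting, λ = 0.693, 2.75 years of follow-up after entry, and gaps uniform on 1 to 11 weeks in both arms. Rejection rates at the nominal 5% level:
- 18 against 18: 5.9% with the gap, 5.9% without.
- 43 against 18: 5.6% with the gap, 5.4% without.

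A gap with the same distribution in both arms makes no material difference to the test.

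**The case against.** The strongest case on the other side has five parts.

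1. **No specified inference is harmed.** Section 14.7 calls all analyses exploratory, and the only historical rate given is for ctDNA clearance. This stands as a limit on importance. It does not make the level of the curves right.
2. **Both arms share the gap.** A reader might infer that the treatment comparison is biased. For the randomized stage 1 patients it is not: the gap precedes allocation, and the simulation agrees. Only the pooled 43 against 18 comparison could be affected, and only if stage 2 patients wait for a different time.
3. **The effect is small against sampling error.** At 50% survival without censoring, the 95% half-width is 1.96 × √(0.25/43) = 15 points with 43 patients and 1.96 × √(0.25/18) = 23 points with 18. This is fair, but the shift always goes one way and costs almost nothing to remove.
4. **The gap may be short.** The 12-week figure is a corner case, the 28-day window may cap the gap at 4 weeks, and the plan does not say whether confirmation means the draw, the report or the eligibility check. All of this stands, and it is why the size is given as a range.
5. **Positivity is a meaningful origin.** It can be, but patients would then have to enter the risk set at Step Two entry, and no delayed entry is planned.

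Two further readings go too far. One is that the gap is event-free by construction for every endpoint. That is strict only for death, because no criterion in section 3.2 explicitly excludes metastasis found on the Step Two CT. The other is that a 50% 12-month DMFS is the protocol's own figure. The statement in section 1.2 concerns any relapse, local or distant, in stage II/III patients, timed from surgery. For DMFS, 50% is therefore towards the pessimistic end.

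**Conclusion.** The point holds for the level of the RFS, DMFS and OS curves under section 14.3 and for any reading of them against outside data. The direction is upward and follows from the text. The size depends on assumptions: a constant hazard, true 12-month DMFS between 80% and 50%, and a gap of 4 to 12 weeks together give about 1.4 to 8.6 points. If the 28-day window governs the draw, the range is 1.4 to 2.7 points or less. The OS shift is close to negligible at the documents' stage II rates.

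A reader might also infer that the primary endpoint or the sample size is compromised. Neither uses these clocks.

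The conflicting RFS definitions, and the missing randomization date for the 25 stage 2 patients, are errors on the face of the text and need no assumption.

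**What to change.** In sections 2.0, 11.0 and 14.3, start RFS, DMFS and OS at one origin: the date of Step Two (On Treatment) registration. Every patient in both stages has this date. Randomization would leave stage 2 patients without a start, and C1D1 would do the same for anyone registered but never dosed. Section 14.6 should say that registered patients who are not dosed are included in these analyses, so that no smaller gap remains between registration and first dose. Report patients who test ctDNA-positive but never enter in the flow chart only.

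The cost is three changed definitions and slightly less favourable survival figures. The date is already recorded at registration, so no new data are needed, and the primary endpoint and sample size are untouched.

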14.4 Statistical Hypotheses

We hypothesize that for ctDNA+ stage II melanoma patients, using atezolizumab and tiragolumab will lead to at least a 25% ctDNA clearance at C3D1, while a null ctDNA clearance rate is 10%.²²

14.5 Sample Size Determination

Under Simon's two-stage optimal design (Simon, 1989), with one-sided alpha = 0.05 and power = 0.8, assuming using atezolizumab and tiragolumab will have a ctDNA clearance rate of 25% and a null rate is 10%, in stage 1, 18 patients will be accrued for the treatment arm (atezolizumab + tiragolumab). If 3 or more patients are observed to be ctDNA-negative at C3D1 for the treatment arm, we will continue the treatment of atezolizumab and tiragolumab to stage 2 with an additional 25 patients being accrued. Otherwise the study will be stopped. If 8 or more ctDNA clearances are observed at the study completion, the combination of atezolizumab and tiragolumab will be considered promising for ctDNA-positive stage II melanoma patients.

Randomization will only happen in the stage 1. In total, 36 patients (18 per arm) will be randomly assigned in a 1:1 ratio to the treatment group (atezolizumab and tiragolumab) or reference group (atezolizumab monotherapy). There is no randomization in stage 2. Stage 2 is single-arm (i.e., the treatment arm only), with a sample size of 25.

According to PI's personal communication with the Natera team, we assume the ctDNA positive rate will be 25%. In stage 1, it is expected that up to 144 patients will be screened in order to randomize 36 patients (18 to each arm). If we continue the study to stage 2 with the treatment arm only, an additional 100 patients will be screened (in order to enroll 25 patients). In total, we expect to accrue 244 patients for ctDNA testing with 61 patients going on to treatment.

14.6 Study Population

If the study stops after stage 1, we will screen 144 melanoma patients who had undergone complete resection. Among them, 18 ctDNA-positive patients being treated with the combination of atezolizumab and tiragolumab will be compared to a historical control and 18 ctDNA-positive patients on atezolizumab monotherapy will be analyzed as a descriptive comparison.

If we continue the study after stage 1, the study will screen 244 patients in total. Among them, 43 ctDNA-positive patients being treated with the combination of atezolizumab and

tiragolumab will be compared to a historical control and 18 ctDNA-positive patients on atezolizumab monotherapy will be analyzed as a descriptive comparison.

14.7 Statistical Analyses

Descriptive statistics will be used to summarize the trial results. Statistics for continuous variables may include means, medians, ranges and appropriate measures of variability. Qualitative variables will be summarized by counts and percentages. The uncertainty of estimates will be assessed by confidence intervals (CIs). All analyses will be considered as exploratory, even if statistical tests will be used.

ctDNA clearance and confirmed negative rate, as well as safety data will be summarized by the number and proportions. RFS, DMFS, and OS will be presented via the Kaplan-Meier method. Median survival and corresponding two-sided 95% CIs will be computed. Survival rates with 95% CIs will be estimated. The group survival difference (i.e., treatment vs. reference) will be examined by the log-rank test. Further exploratory correlative analyses will be performed via Fisher exact test, t-test, or nonparametric Wilcoxon–Mann–Whitney test, if needed.

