14.0 STATISTICAL CONSIDERATIONS

14.1 Study Design

This is an open-label, multi-center, Simon two-stage phase II study consisting of random allocation of a portion of patients to a small reference arm to offer some protection against the uncertainties and potential biases of a one-armed study while retaining some of the statistical efficiency. The reference arm is not a control group in the traditional sense and there will not be a formal efficacy comparison between the treatment and reference groups (Herson and Carter, 1986; Rubinstein, et. al., 2009).

The purpose of this study is to evaluate the efficacy and safety of atezolizumab and tiragolumab in stage II melanoma patients who had undergone complete resection and been tested positive for circulating tumor DNA (ctDNA). In this study, the treatment arm (i.e., atezolizumab and tiragolumab) will not be compared with the reference arm (i.e., atezolizumab only); it will be analyzed against historical control as a one-armed study. The reference arm is intended to only act as a check on the similarity of the current patients to the historical control for a descriptive estimation of ctDNA clearance.

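### The exploratory treatment-versus-reference log-rank test names no analysis set, and RFS has two start dates, one of which stage 2 patients do not have

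*Combined protocol and SAP*

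**What the plan says.** **The test.** Section 14.7 presents RFS, DMFS and OS by Kaplan-Meier, then states: "The group survival difference (i.e., treatment vs. reference) will be examined by the log-rank test". It gives no analysis set, significance level or sidedness. The same section adds: "All analyses will be considered as exploratory, even if statistical tests will be used".

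**Purpose of the reference arm.** Section 14.1 says "there will not be a formal efficacy comparison between the treatment and reference groups" and that the treatment arm is analysed against a historical control. The endpoint table in Section 2 says otherwise for two endpoints: "The secondary efficacy objective of this study is to compare DMFS between the two treatment arms" and "The secondary efficacy objective of this study is to compare OS between the two treatment arms".

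**Who is in each group.** Stage 1 randomises 36 patients, 18 per arm. The condition for stage 2 in 14.5 is "If 3 or more patients are observed to be ctDNA-negative at C3D1 for the treatment arm". Stage 2 then adds 25 patients, all on the combination and none randomised (14.5 and 4.5). For that case 14.6 counts "43 ctDNA-positive patients being treated with the combination of atezolizumab and" tiragolumab, set against a historical control, while "18 ctDNA-positive patients on atezolizumab monotherapy will be analyzed as a descriptive comparison".

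**RFS start date.** Sections 2 and 11 start RFS at randomization. Section 14.3 starts it when positive ctDNA is confirmed. DMFS and OS start at ctDNA confirmation in both Section 2 and 14.3, so the conflict concerns RFS only.

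**The concern.** Nothing ties the log-rank test to either group size in 14.6. A 43 versus 18 test would set a group that is 25/43 = 58% unrandomised and later-enrolled against a reference group recruited only in stage 1. If prognosis shifts between stages, the result is biased in the direction of the shift. Eligibility is the same in both stages, but Section 4.6 plans added sub-sites at 6 and 12 months, so the site mix can change. Section 5.3 also replaces early discontinuers in stage 1 only.

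The RFS conflict is the firmer defect. The definition in Sections 2 and 11 cannot be computed for a stage 2 patient, so it affects the planned Kaplan-Meier curves, medians and survival rates even if no test is run. Two analysts could report different contrasts and different RFS from the same data.

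**Working it through.** **1. The plan's own design.** The documents give no event count or power for the log-rank test. The primary two-stage design does reproduce. With b(x) the binomial probability of x clearances among 18, P(promising) = Σ over x ≥ 3 of b(x) × P(Bin(25, p) ≥ 8 − x). This is 0.0480 at p = 10% and 0.8003 at p = 25%, against the stated 0.05 and 0.80.

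**2. How often stage 2 opens.** P(X ≥ 3 of 18) = 1 − P(0) − P(1) − P(2).
- p = 10%: 1 − (0.1501 + 0.3002 + 0.2835) = 0.266
- p = 25%: 1 − (0.0056 + 0.0338 + 0.0958) = 0.865

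**3. Effect of drift on the pooled test.** RFS was simulated with no treatment effect: 18 reference, 18 stage 1 combination and 25 stage 2 combination patients. The assumptions are exponential times, censoring at 33 months (5.7 ends follow-up 3 years from surgery), rejection at |z| > 1.96 counted per direction, and 100,000 trials per scenario. Results for 43 versus 18 at an assumed 60% one-year relapse:

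| Stage 2 hazard ÷ stage 1 hazard | Favours combination | Favours reference |
|---|---|---|
| 0.5 | 0.291 | 0.000 |
| 0.7 | 0.124 | 0.003 |
| 0.8 | 0.082 | 0.007 |
| 0.9 | 0.053 | 0.013 |
| 1 | 0.036 | 0.023 |
| 1.11 | 0.023 | 0.036 |
| 1.25 | 0.014 | 0.058 |
| 1.43 | 0.007 | 0.091 |
| 2 | 0.001 | 0.204 |

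18 versus 18 gives 0.031 and 0.030. At 40% one-year relapse, 43 versus 18 favours the combination in 0.233, 0.110, 0.074, 0.050 and 0.034 for multipliers 0.5 to 1. It favours the reference in 0.021, 0.034, 0.053, 0.085 and 0.203 for multipliers 1 to 2. 18 versus 18 gives 0.028 each way.

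**4. Conditioning on stage 2 having opened.** The go rule selects on the same 18 combination patients. With no drift, no treatment effect, marginal one-year relapse of 60% and 60,000 trials, each cell gives favours combination / favours reference:

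| Clearance | Assumed hazard, clearers ÷ non-clearers | 18 vs 18 | 43 vs 18 |
|---|---|---|---|
| 10% | 0.5 | 0.042 / 0.018 | 0.042 / 0.017 |
| 10% | 0.3 | 0.050 / 0.010 | 0.047 / 0.014 |
| 10% | 0.1 | 0.062 / 0.003 | 0.051 / 0.008 |
| 25% | 0.5 | 0.032 / 0.025 | 0.037 / 0.020 |
| 25% | 0.3 | 0.033 / 0.021 | 0.038 / 0.018 |
| 25% | 0.1 | 0.033 / 0.014 | 0.037 / 0.017 |

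**5. Precision.** At hazard ratio 1 and 60% one-year relapse, the standard error of the log hazard ratio is 0.357 for 18 versus 18 (33 events) and 0.298 for 43 versus 18 (56 events). The 95% intervals are exp(±1.96 × 0.357) = 0.50 to 2.01 and exp(±1.96 × 0.298) = 0.56 to 1.79.

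**6. Start date.** Take 12-month RFS of 40% from randomization, so the hazard is −ln(0.4)/12 = 0.0764 per month. If the interval before randomization is event-free, RFS at 12 months from ctDNA confirmation is exp(−0.0764 × (12 − gap in months)). This is 0.400, 0.414 and 0.429 for gaps of 0, 2 and 4 weeks. The outer bound is 12 weeks (draw from week 4, randomization by week 16), which gives 0.494.

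**The case against.** The strongest reply is that nothing rests on this test. Section 14.7 labels everything exploratory, 14.1 rules out a formal comparison, 14.6 calls the reference patients descriptive, and no passage prescribes 43 versus 18. All of that stands and limits the weight of the point. It does not supply a population or a start date.

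The drift sizes are assumed. The largest rates need a halved or doubled hazard, and a 10% change gives only about 4–5%. The drift runs are also not conditioned on stage 2 opening. This stands: the figures show direction and sensitivity, not an expected bias.

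Restriction is not free even without drift. At 10% clearance, 18 versus 18 can be slightly worse once stage 2 has opened (6.2% against 5.1% at the extreme), because the go rule selects on those patients. That also stands, though it is small, and at 25% clearance the order reverses.

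The 12-week gap overstates the start-date effect. The clock in 14.3 starts at confirmation, not at the draw, so assay turnaround shortens it. The calendar's general 28-day Step 2 screening window, if it governs the draw despite that item's own footnote, would cap the gap at about 4 weeks (43%). A shift of 1 to 3 points is the more realistic reading.

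Finally, randomization is the usual origin for a randomised contrast, and two of the three RFS passages use it. It still cannot serve stage 2.

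**Conclusion.** The concern holds. RFS as defined in Sections 2 and 11 cannot be computed for 25 of the 43 combination patients and conflicts with 14.3. The log-rank test in 14.7 has no analysis set, and Section 2 states an arm comparison that 14.1 disclaims.

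The consequence is moderate and conditional. It arises only if stage 2 opens (probability 0.27 to 0.86 across the design rates). Without drift, pooling is close to nominal. With an assumed stage 2 hazard of 0.7 or 1.43 times stage 1, a pooled test at 60% one-year relapse wrongly favours one arm in 12% or 9% of trials, against about 3% for the randomised set. These rates depend on the assumed relapse rate, exponential times and drift. DMFS and OS were not simulated. The primary endpoint and the stage 2 decision are untouched. The wording should be settled before survival data are analysed.

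**What to change.** 1. **Section 14.7.** State that any log-rank test or hazard ratio (with 95% CI) for treatment versus reference is exploratory and includes only patients randomised in stage 1, analysed as randomised, including any later replaced under 5.3. Show stage 2 and pooled combination patients as single-arm Kaplan-Meier curves.
2. **Sections 2 and 11.** Start RFS when positive ctDNA is confirmed, in both stages, as 14.3 already does; DMFS and OS need no change. Step Two registration, applied to both stages, would also work. The origin must not differ by stage.
3. **Sections 2 and 14.1.** Say in both places that the stage 1 contrast is exploratory and supports no efficacy decision.

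This is protocol and SAP wording only, with no new data. Item 1 costs precision: an interval of about 0.50 to 2.01 instead of 0.56 to 1.79 under the assumptions above. Those figures are approximate, because the coin-toss randomization in 4.5 need not give exactly 18 and 18 and replaced patients stay in the set. Item 2 leaves a short, presumably event-free period before enrolment in RFS, equal in expectation between the randomised arms.

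These changes do not address Sections 5.6 and 5.7, which end follow-up after recurrence and separately limit OS, and DMFS after a non-distant relapse.
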